7.3 Randomization

Refer to Section 9.3 of the CSP for details.

7.4 Replacement

Refer to Section 9.11 of the CSP for details.

7.5 Blinding and Unblinding

Refer to Section 10.7 of the CSP for details.

8 ANALYSIS SETS

The following analysis sets are defined: All Subjects Set, Full Analysis Set (FAS), and Safety Set.

8.1 All Subjects Set

The **All Subjects Set** will include all subjects who were randomized or received at least 1 dose of study drug. This analysis set will be used for all individual subject data listings and disposition summary tables, unless otherwise specified.

8.2 Full Analysis Set

The **FAS** will include all randomized subjects who received at least 1 dose of study drug. The FAS will be used to summarize subject demographics and background characteristics, and for all efficacy analyses, unless otherwise specified. Subjects will be analyzed according to the treatment to which they were randomized.

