Randomization	X									Randomization may occur up to 7 days before Day 1 after all eligibility criteria including antigenic AAT levels <8 µM are confirmed. If randomization occurs before Day 1, eligibility must also be confirmed before the first dose of study drug on Day 1.
Clinic visit	X									
Clinic or home health visit		X	X	X	X	X	X	X	X	Subjects will have the option to complete these visits in the clinic or to have a home health visit. Home health visits are only an option if they receive approval from both ethical and regulatory authorities in the respective country.
Telemedicine video conference or telephone contact		X	X	X	X	X	X	X	X	Performed within 1 day after home health visit. Required only for subjects who have a home health visit; not required for subjects who have a clinic visit.
Antigenic AAT level	X	X	X		X	X	X	X	X	Section 11.3
Functional AAT level	X	X	X		X	X	X	X	X	Section 11.3

Table 3-3 Study VX19-864-101: Treatment Period and Follow-up Visits

Event/ Assessment	Treatment Period					VX-864 Washout Visit 7 (±2) Days After Last Dose of Study Drug	ETT Visit ^e	Safety Follow-up Visit 14 (±2) Days After Last Dose of Study Drug	Safety Follow-up Visit 28 (±2) Days After Last Dose of Study Drug	Comments
	Day 1 ^a	Day 7 (±1) ^b	Day 14 (±2) ^b	Day 21 (±2) ^b	Day 28 (-2) ^c					
Weight and height	X									Measured with shoes off.
Standard 12-lead ECG	X	X			X		X	X	X	Performed in triplicate after the subject has rested for at least 5 minutes When ECGs, vital signs, and blood draws are done on the same day, they should be performed in said order. Day 1: predose and 6 hours (±15 min) after dosing. Section 11.5.4
Vital signs	X	X	X		X		X	X	X	Performed after the subject has rested for at least 5 minutes. Section 11.5.3

Table 3-3 Study VX19-864-101: Treatment Period and Follow-up Visits

Event/ Assessment	Treatment Period					VX-864 Washout Visit 7 (±2) Days After Last Dose of Study Drug	ETT Visit ^e	Safety Follow-up Visit 14 (±2) Days After Last Dose of Study Drug	Safety Follow-up Visit 28 (±2) Days After Last Dose of Study Drug	Comments
	Day 1 ^a	Day 7 (±1) ^b	Day 14 (±2) ^b	Day 21 (±2) ^b	Day 28 (-2) ^c					
Pulse oximetry	X	X	X		X		X	X	X	Performed after the subject has rested for at least 5 minutes. Section 11.5.3
Pregnancy test (premenopausal female subjects of childbearing potential only)	Urine and serum		Serum		Urine		Serum	Serum	Serum	Subjects must have a negative urine pregnancy test result on Day 1 before dosing administration.

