8 STUDY POPULATION

Eligibility will be reviewed and documented by an appropriately qualified member of the investigator's team before subjects are randomized and will also be confirmed before the first dose of study drug on Day 1.

Subjects who meet all of the inclusion criteria and none of the exclusion criteria will be eligible.

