8.1 Inclusion Criteria

1. Subject will sign and date an informed consent form (ICF).
2. Willing and able to comply with scheduled visits, treatment plan, study restrictions, laboratory tests, contraceptive guidelines, and other study procedures.
3. Subjects will be 18 through 80 years of age, inclusive, at the time of signing of the ICF.
4. All female subjects must have a negative pregnancy test at screening (serum test). Premenopausal female subjects of child-bearing potential must also have a negative pregnancy test on Day 1 (urine test) and must not be breastfeeding or planning to become pregnant during the study or within 90 days after the last study drug dose.
5. Body mass index (BMI) of 18.0 to 35.0 kg/m², inclusive.
6. Subjects must have a *PiZZ* genotype confirmed at screening.

NOTE: *PiZZ* genotype must be tested at the central laboratory. Historical genotype results can be used to determine eligibility if they were obtained as part of a different Vertex study. In addition, if the screening *PiZZ* genotype result is not received before randomization, a previous non-Vertex *PiZZ* genotype laboratory report (approved by the medical monitor or designee) may be used to establish provisional eligibility. **Subjects who have been randomized and whose screening genotype subsequently does not confirm study eligibility must be discontinued from the study (Section 9.10).**

7. Plasma antigenic AAT level <8 µM during screening.

NOTE: For subjects who have been on augmentation therapy at any time, results used to confirm eligibility must be drawn >42 days after the last dose of augmentation therapy. Antigenic AAT levels must be obtained from the central laboratory and results confirmed before randomization.

8. Willing to remain off of augmentation therapy from >42 days before antigenic AAT levels are obtained for eligibility through the last Safety Follow-Up Visit.

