9.10 Removal of Subjects

Subjects may withdraw from the study at any time at their own request. Subjects may be withdrawn from study drug treatment at any time at the discretion of the investigator or Vertex for safety, behavior, noncompliance with study procedures, or administrative reasons. A subject who withdraws from study drug treatment will continue to be followed unless the subject withdraws consent.

Subjects who are withdrawn from study drug dosing will complete assessments as described in [Section 9.1.4](#).

Subjects who have been randomized and whose screening *PiZZ* genotype does not confirm study eligibility must be discontinued from the study, even if a previous *PiZZ* genotype laboratory report was used to establish eligibility.

If a subject does not return for a scheduled visit, reasonable effort will be made to contact the subject. In any circumstance, reasonable effort will be made to document subject outcome. The investigator will inquire about the reason for withdrawal, request that the subject return all unused investigational product(s), request that the subject have a Safety Follow-up Visit, if applicable (see [Section 9.1.4](#)), and follow up with the subject regarding any unresolved AEs.

If a subject withdraws consent for the study, no further assessments will be performed. Vertex may retain and continue using the study data and samples after the study ends and may use the samples and information in the development of the study compound, for other drugs and diagnostics, in publications and presentations, and for education purposes. If a subject withdraws from the study, the study data and samples collected will remain part of the study. A subject will not be able to request the withdrawal of his/her information from the study data. A subject may request destruction of the samples collected from him/her during the study as long as those samples can be identified as his/her samples.

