9.11 Replacement of Subjects

Subjects who withdraw or are withdrawn before the first dose of study drug may be replaced.

Subjects who withdraw or are withdrawn for nonsafety reasons during the study drug treatment period(s) may be replaced at Vertex's discretion.

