12.1 Sample Size and Power

Subjects will be randomized 2:1:1:1 to receive VX-864 500 mg q12h (n = 16), VX-864 300 mg q12h (n = 8), VX-864 100 mg q12h (n = 8), or placebo (n = 8).

Assuming 10% of the randomized subjects have a missing value at Day 28, this sample size provides adequate precision to estimate the absolute plasma functional AAT levels at Day 28 for the VX-864 500 mg q12h dose group.

Information regarding the sample size assessments is provided below.

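### Does the plan need a separate analysis rule for a dosed subject whose screening genotype later fails to confirm PiZZ?

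*SAP*

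**What the plan says.** Inclusion criterion 6 (Protocol 8.1) calls for central-laboratory genotyping at screening. If the result is not back by randomisation, a prior report from outside the sponsor's studies, approved by the medical monitor or designee, "may be used to establish provisional eligibility". The criterion continues: "Subjects who have been randomized and whose screening genotype subsequently does not confirm study eligibility must be discontinued from the study". Protocol 9.10 repeats this for subjects whose screening PiZZ "genotype does not confirm study eligibility must be discontinued from the study, even if a previous" report had been relied on.

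Eligibility has to be checked again before dosing. Protocol 8 says it "will also be confirmed before the first dose of study drug on Day 1", and the randomisation row of Table 3-3 says "If randomization occurs before Day 1, eligibility must also be confirmed before the first dose of study drug on Day 1". Neither place says whether provisional eligibility satisfies that check.

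On analysis, the FAS "will include all randomized subjects who received at least 1 dose of study drug" (SAP 8.2; Protocol 12.2 agrees). SAP 9.3 bases every efficacy analysis on it unless something else is specified. SAP 9.3.1.2 fits the observed changes at Days 7, 14 and 28, assumes missing at random and imputes nothing. The one visible analysis that drops AAT values (SAP 9.1) is optional and concerns PEx and COVID-19 vaccination. Important deviations are summarised (SAP 9.2.6), with no visible exclusion attached. Under Protocol 9.11, subjects "withdrawn for nonsafety reasons during the study drug treatment period(s) may be replaced at" the sponsor's discretion.

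**The concern.** The protocol foresees a subject entering on a provisional genotype and then failing the central test, and says what happens to that subject in the clinic. The visible SAP says nothing specific about that subject's data. Read together, the two documents remove the subject from the study for being outside the target population but leave the subject's early AAT values in an estimate meant to describe PiZZ subjects.

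Three of the four arms are planned at eight subjects, so one subject is not negligible. Genotype is fixed before randomisation, so an exclusion based on a pre-dose sample and decided blind would not introduce treatment-related selection. It is natural to ask why the plan does not provide for one, and whether silence leaves the choice open until the case, and perhaps the data, are known.

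**Working it through.** **Is the case left undecided?** There are two readings of the pre-dose check.

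- If provisional eligibility does not satisfy it, the subject should not be dosed before the central result. An undosed subject is outside the FAS and may be replaced under Protocol 9.11.
- If provisional eligibility does satisfy it, a dosed subject is in the FAS, and SAP 9.3 puts any usable AAT values into the MMRM.

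Each reading gives one answer, fixed before unblinding. Protocol 9.10 points the same way for withdrawals: data gathered up to that point stay with the study.

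**What has to happen.** The central genotype must be late. The approved prior report must be wrong. The central antigenic AAT must still be below 8 µM, confirmed before randomisation. Dosing must precede the genotype result, and at least one post-baseline AAT sample must be drawn before that result arrives. Protocol 11.3 tells sites to allow at least 14 days for the AAT result. If genotype blood is drawn with that sample (an assumption), it has been with the laboratory about 14 days at randomisation. With randomisation on Day 1, it has been there about 14 + 5 = 19 days at the earliest Day 7 visit (Day 6), and 14 + 25 = 39 days at the earliest Day 28 visit (Day 26).

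**Arm sizes.** Allocating 40 subjects 2:1:1:1 gives 40 × 2/5 = 16 and 40 × 1/5 = 8, 8, 8. Two parts of 20 at 2:2:1 give 8 + 8, 8, 8 and 4 + 4. Both match the stated 16, 8, 8 and 8.

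**Weight of one such subject in the arm's Day 28 mean.** The documents give no covariance. I assume equal variances and a common correlation r between visits, from 0.3 to 0.9, with all other subjects complete. The planned covariance is unstructured, so this is an illustration.

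| Data from the subject | Formula | n = 16 | n = 8 |
|---|---|---|---|
| No post-baseline value | 0 | 0 | 0 |
| Day 7 only | r/n | 1.9% to 5.6% | 3.8% to 11.3% |
| Days 7 and 14 | 2r/((1 + r)n) | 2.9% to 5.9% | 5.8% to 11.8% |
| Through Day 28 | 1/n | 6.3% | 12.5% |

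The last row needs the genotype still outstanding at about Day 28, because a failed result ends participation.

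**With the planned missingness.** Protocol 12.1 works from "Assuming 10% of the randomized subjects have a missing value at Day 28". Counting only subjects with a Day 28 value gives 1/14.4 = 6.9% and 1/7.2 = 13.9%. These are upper bounds, because the MMRM also uses early visits from subjects who miss Day 28. If those subjects have Days 7 and 14, and m = 0.9n have Day 28, the weight is 1/m − (2r/(1 + r)) × (1/m − 1/n). For n = 8:

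- r = 0.3: 0.1389 − 0.4615 × 0.0139 = 13.2%
- r = 0.9: 0.1389 − 0.9474 × 0.0139 = 12.6%

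For n = 16 the values are half of these, 6.6% and 6.3%.

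**From weight to shift.** With complete data from the others, the shift is the weight times the subject's difference from the rest of the arm. For Day 7 data only and n = 8, each 1 µM of difference at Day 7 moves the Day 28 mean by 0.04 to 0.11 µM. The documents do not give that difference. The 8 µM ceiling limits the screening antigenic level but not the response.

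**Cost of excluding instead.** Using √(1/a + 1/p) with complete data, the standard error of a difference from placebo rises as follows when one subject is dropped:

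- from the 500 mg arm: √((1/15 + 1/8)/(1/16 + 1/8)) = 1.011
- from either side of a 300 mg or 100 mg comparison: √((1/7 + 1/8)/(1/8 + 1/8)) = 1.035
- from placebo in the 500 mg comparison: √((1/16 + 1/7)/(1/16 + 1/8)) = 1.047

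**The case for a change.** The best argument for acting is that the protocol names this case twice and the visible SAP never does. The general FAS rule may not have been chosen with it in mind. A blind exclusion based on a pre-dose sample is free of treatment-related selection, would match the stated population, and would cost 1% to 5% in standard error. One extra model run would show whether the subject mattered. Replacement would not settle it, since it is discretionary and nothing visible says how a replaced subject's data are handled.

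Much of this stands. No genotype-specific efficacy rule or supporting analysis is visible, and exclusion would be defensible. Two limits apply. Text is redacted after the model description in Protocol 12.3.3.1, and SAP Appendices A and D and the Protocol Deviation Plan are not available, so absence from the whole plan cannot be established. More importantly, the argument shows that exclusion is possible, not that retention is wrong. Anyone content with the FAS as primary and exclusion as a sensitivity run has already accepted the primary analysis as written. Such a run can be added before unblinding if a case occurs.

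The unclear status of provisional eligibility is a separate matter of conduct. Protocol 9.10 speaks of a prior report establishing eligibility without the word provisional, which favours reading it as enough for enrolment. Neither reading leaves the analysis undefined.

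**Conclusion.** No change is needed. The plan has a rule, set in advance: a randomised and dosed subject stays in the efficacy analysis, and values collected before discontinuation are used. Keeping everyone randomised and dosed is a fair trade-off against a narrower, genotype-confirmed population.

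The case depends on several unlikely steps in sequence. If it did occur with early visits only, one subject would carry roughly 2% to 6% of the Day 28 mean at n = 16, or 4% to 12% at n = 8. The weight would reach 6.3% or 12.5%, slightly more with missing data elsewhere, only if the genotype were still outstanding at about Day 28. The early-visit figures rest on equal variances, correlations of 0.3 to 0.9 and complete data from the other subjects. None of them is a bias, because nothing in the documents gives the subject's difference from the arm. An analysis without the subject would be a reasonable optional addition if the case arose. Its absence now is not a defect.

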8.3 Safety Set

The **Safety Set** will include all subjects who received at least 1 dose of study drug. The Safety Set will be used for all safety analyses in which subjects will be analyzed according to the treatment they received, unless otherwise specified.

9 STATISTICAL ANALYSIS

9.1 General Considerations

The Schedule of Assessments is provided in Section 3 of the CSP. The precision standards for reporting safety variables are provided in an internal Biometrics document that specifies programming rules including the precision for derived variables.

Continuous variables will be summarized using the following descriptive summary statistics: the number of subjects (n), mean, SD, median, minimum value (min), and maximum value (max).

Categorical variables will be summarized using counts and percentages.

Baseline value, unless specified otherwise, will be defined as the most recent non-missing measurement (scheduled or unscheduled) collected before the first dose of study drug. For

ECGs, the baseline value will be defined as the average of the non-missing pre-dose measurements (triplicate) collected before the first dose of study drug. For subjects who have ever been on augmentation therapy at any time, only functional and antigenic AAT levels collected >42 days after the last dose of augmentation therapy can be used to define baseline values. For antigenic AAT levels, only the screening results obtained from the on-treatment assay can be used to define baseline values if the Day 1 pre-dose results are missing.

Change (absolute change) from baseline will be calculated as post-baseline value – baseline value.

Relative change from baseline will be calculated and expressed in a percentage as $100\% \times (\text{post-baseline value} - \text{baseline value})$ /baseline value.

Treatment-emergent (TE) Period will include the time period starting from the date of the first dose of study drug to either (1) Safety Follow-up Visit 28 days after the last dose of study drug, (2) Early Termination of Treatment (ETT) Visit if it replaces the Safety Follow-up Visit 28 days after the last dose of study drug, or (3) 28 days after the last dose date for subjects who do not have a Safety Follow-up Visit 28 days after the last dose or an equivalent ETT.

Unscheduled visits: Data obtained from unscheduled visits will be included in the analysis as follows:

- In scheduled visit windows per specified visit windowing rules
- In the derivation of baseline and last on-treatment measurements
- In the derivation of maximum and minimum values during the TE period, and maximum and minimum change from baseline values during the TE period for safety analyses
- In individual subject data listings as appropriate

Incomplete or missing data will not be imputed, unless specified otherwise.

Outliers: No formal statistical analyses will be performed to detect and/or remedy the presence of statistical outliers, unless specified otherwise.

Additional considerations:

- For all model-based assessments, a dose group will only be included if ≥3 subjects have non-missing data available.
- An individual subject data listing will be provided for subject visits impacted by COVID-19.

• If appropriate and if needed, additional analysis of the functional and antigenic AAT endpoints may be performed excluding any AAT measurements influenced by a PEx and/or a COVID-19 vaccination.

All individual subject data will be presented in individual subject data listings based on the All Subjects Set.

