9.9 Study Drug Interruption and Stopping Rules

The investigator has the discretion to discontinue study drug treatment at any time if the investigator feels that the subject's continued participation in the study jeopardizes their safety.

Any subject with worsening of AATD or disease progression that, in the judgement of the treating physician, requires (re)initiation of standard of care treatment (per local guidelines) that is prohibited in this study (including augmentation therapy) will discontinue study drug treatment.

Any subject with QTcF values above the threshold values as described in Section 11.5.4 will discontinue study drug treatment.

Study drug treatment may be interrupted for safety concerns at discretion of the investigator.

Study drug administration must be interrupted immediately (before confirmatory testing), and the medical monitor must be notified, if any of the following criteria are met:

- ALT or AST $>5 \times$ ULN
- Total bilirubin $>3 \times$ ULN
- ALT or AST $>3 \times$ ULN associated with total bilirubin $>2 \times$ ULN and/or clinical jaundice

Subjects with new treatment-emergent ALT or AST elevations of $>3 \times$ ULN, or total bilirubin $>2 \times$ ULN, must be followed closely, including confirmatory testing performed within 48 to 72 hours of the initial finding and there must be close monitoring of ALT, AST, and bilirubin levels thereafter, as clinically indicated.

If a subject cannot return to the site for confirmatory testing, a local laboratory may be used. Local laboratory results must be reported immediately to the medical monitor, and the subject must have the tests repeated and sent to the central laboratory as soon as possible (ideally within 48 to 72 hours).

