9.3.1.2 Primary Analysis

The primary analysis of the primary efficacy variable includes data from VX-864 treatment groups and the placebo group. The primary comparison consists of the pairwise comparison between each dose of VX-864 and placebo.

The primary analysis will be based on a mixed-effects model for repeated measures (MMRM) with change from baseline at Days 7, 14, and 28 as the dependent variable. The MMRM model will include the treatment group, visit, and treatment-by-visit interaction as fixed effects. An unstructured covariance structure will be used to model the within-subject errors. If the model estimation does not converge, a compound symmetry covariance structure will be used instead. The model will be estimated using restricted maximum likelihood. Denominator degrees of freedom for the F-test for fixed effects will be estimated using the Kenward-Roger approximation. Conditional on the observed data and covariates, missing data will be assumed to be missing at random; consequently, no imputation of missing data will be performed.

The primary result obtained from the model will be the estimated treatment difference between each VX-864 treatment group in the model and the placebo group at Day 28. The adjusted means with 2-sided 95% confidence intervals and 2-sided *P* values will be provided. In addition, the estimated treatment differences, obtained from the model, between each VX-864 treatment group

in the model and the placebo group at each post-baseline visit will be provided, along with 2-sided 95% confidence intervals and 2-sided *P* values.

The observed values and change from baseline of functional AAT levels will also be summarized descriptively by treatment group at each visit.

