9.3.2.2 Analysis Method

The analysis of the secondary efficacy variable includes data from VX-864 treatment groups and the placebo group.

Analysis of the secondary efficacy variable will be based on an MMRM similar to the primary analysis of the primary efficacy variable, with change from baseline in plasma antigenic AAT levels at Days 7, 14, 28 as the dependent variables and the treatment group, visit, and treatment-by-visit interaction as fixed effects. The adjusted means and the estimated treatment differences obtained from the model between each VX-864 treatment group in the model and the placebo group at Day 28, as well as at each post-baseline visit, will be provided, with 2-sided 95% confidence intervals and 2-sided *P* values.

The observed values and change from baseline of the antigenic AAT levels will be summarized descriptively by treatment group at each visit.

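### In the visible SAP, the 42-day augmentation rule protects baseline AAT only; if a subject restarts augmentation, infused AAT could enter the Day 7, 14 or 28 analysis as response (rare, low priority)

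*SAP*

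**What the plan says.** - **Baseline.** For subjects who have ever had augmentation, SAP 9.1 states that "only functional and antigenic AAT levels collected >42 days after the last dose of augmentation therapy can be used to define baseline values".
- **Primary model.** SAP 9.3.1.2 fits an MMRM "with change from baseline at Days 7, 14, and 28 as the dependent variable". The covariance is unstructured, with compound symmetry as the fallback on non-convergence. No separate covariance by arm is stated, so I read it as shared by all arms.
- **Secondary model.** SAP 9.3.2.2 uses a similar model "with change from baseline in plasma antigenic AAT levels at Days 7, 14, 28 as the dependent variables".
- **Analysis set.** Both use the FAS: "Subjects will be analyzed according to the treatment to which they were randomized" (SAP 8.2).
- **Other rules that might catch a distorted value.** On outliers, SAP 9.1 says: "No formal statistical analyses will be performed to detect and/or remedy the presence of statistical outliers, unless specified otherwise". It also allows an optional additional analysis "excluding any AAT measurements influenced by a PEx and/or a COVID-19 vaccination"; augmentation is not named. Unscheduled results are used "In scheduled visit windows per specified visit windowing rules"; those rules are not in the public text.
- **Restart of augmentation.** Under protocol 9.9, a subject whose worsening disease calls for standard treatment "prohibited in this study (including augmentation therapy) will discontinue study drug treatment". Protocol 9.10 keeps such subjects in follow-up unless they withdraw consent.
- **Visits after early stopping.** Protocol 9.1.2 asks for the assessments of every study visit and points to 9.1.4. Section 9.1.4 and Table 3-3 footnote e name only the ETT and Safety Follow-up Visits. Table 3-3 schedules AAT at the ETT, washout and follow-up visits as well as at Days 7, 14 and 28.

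**The concern.** The baseline rule shows that the sponsor regards an AAT value taken within 42 days of augmentation as unusable. The same value after baseline is just as uninformative about VX-864, yet no visible rule keeps it out of either MMRM. The missing-at-random statement covers absent values, not observed ones that carry infused protein.

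An affected subject on an active dose makes that dose look better. An affected placebo subject makes all three doses look worse, because placebo is the comparator for each. Three of the four arms have 8 subjects, so a single value carries weight. The shared covariance also passes the extra variance to comparisons that do not involve the affected arm.

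**Working it through.** **The plan's own figures.** Forty subjects at 2:1:1:1 give 40 × 2/5 = 16 and 40 × 1/5 = 8, 8, 8. Two blocks of 20 at 2:2:1 give 8, 8, 4 each, so the totals agree. The steady-state figure in protocol 9.4.1 also holds: 1 − 2^(−28/5) = 97.9%, above the stated 95%. The sample-size statement on precision carries no visible number, so it cannot be checked.

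**Does 42 days separate clean from affected values?** With the protocol's AAT half-life of about 5 days, assumed to apply to infused AAT, the share of the rise that remains is 2^(−7/5) = 38% at 7 days, 2^(−14/5) = 14% at 14 days and 2^(−42/5) = 0.3% at 42 days. A restart on or after Day 1 is at most 27 days before Day 28, so every later value in the models falls inside the 42-day limit.

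**Effect of one Day 28 value raised by k residual SDs.** With complete data, the unstructured model reduces at each visit to a four-arm comparison with pooled variance on 40 − 4 = 36 df.

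- Arm-mean bias = k/n.
- Interval width ratio = √(1 + k²(1 − 1/n)/36).
- Clean half-width, 500 mg minus placebo = t(0.975, 36) × √(1/16 + 1/8) = 0.878 SD.

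| k | bias, n = 8 | bias, n = 16 | width ratio (value in an arm of 8) | half-width, 500 mg − placebo |
|---|---|---|---|---|
| 2 | 0.250 SD | 0.125 SD | 1.05 | 0.920 SD |
| 3 | 0.375 SD | 0.188 SD | 1.10 | 0.969 SD |
| 5 | 0.625 SD | 0.312 SD | 1.27 | 1.113 SD |
| 10 | 1.250 SD | 0.625 SD | 1.85 | 1.627 SD |

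**Which visits are affected?** Simulation (within-subject correlation 0.6, assumed) and REML fits with 10% of Day 28 values missing agree. Under the unstructured covariance, a Day 28 value leaves the Day 7 and Day 14 intervals unchanged (× 1.00). Under compound symmetry, all visits widen: × 1.04, 1.10 and 1.35 for k = 3, 5 and 10.

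**Illustration in µM, on assumed inputs.** Take a rise of 5–15 µM and a Day 28 SD of 1–2 µM; neither is a document figure.

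- Arm-mean shift: 5/8 to 15/8 = 0.6–1.9 µM (n = 8), or 5/16 to 15/16 = 0.3–0.9 µM (n = 16).
- Half-width for 500 mg minus placebo, value in an arm of 8: from 0.88 to 1.11–2.23 µM (SD 1), or from 1.76 to 1.89–2.70 µM (SD 2).

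With no true effect (nominal 2.5% in each direction; 100,000 simulated trials per setting; Day 28 pooled t-test), and given that one subject is affected:

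- On 500 mg, that dose looks falsely better in 0.2–3.9% of trials.
- On 300 or 100 mg, the affected dose looks falsely better in 6.9–11.9%.
- On placebo, 500 mg looks falsely worse in 8.0–21.6%.

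**Cost of dropping the value (standard-error ratio).**

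- Subject on 500 mg, against placebo: √(1/15 + 1/8)/√(1/16 + 1/8) = 1.011.
- Subject on 300 or 100 mg, against placebo: √(1/7 + 1/8)/√(1/8 + 1/8) = 1.035.
- Placebo subject, 500 mg against placebo: √(1/16 + 1/7)/√(1/16 + 1/8) = 1.047. The REML fits, which borrow from earlier visits, give 1.03.

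For a placebo subject, dropping the value gives a half-width of 0.920 SD for 500 mg against placebo, the same as keeping a value shifted by 2 SD. Beyond that, dropping is also the more precise choice.

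**The case against.** The asymmetry has a reason. Screening plans a draw that may fall 42 days or less after augmentation and then a second draw, so baseline needs a rule. No post-baseline draw is planned under augmentation, which is prohibited until the last Safety Follow-up assessments are complete. This explains the baseline rule but does not say what to do with a subject who restarts.

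The harm also depends on text that is not public. SAP 9.1 refers to specified windowing rules, the visible appendices are only B, C and E, and text is redacted after the primary model in protocol 12.3.3.1. This stands: a reader might infer that the plan has no rule, but the documents show only that none is visible.

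The route into the model is narrow. Protocol 9.1.4 does not list Days 7, 14 or 28 after early stopping, and an ETT Visit held promptly may come before any infusion. This stands in part, because 9.1.2 can be read more widely and off-schedule results are windowed.

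Keeping all observed data as randomized is a recognised treatment-policy approach. That is fair, and such an analysis should be kept. As the main analysis, however, it would credit the study arm with the infused endpoint protein itself, and the visible text does not present it as a deliberate choice.

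Finally, medication dates are recorded, and a biostatistician without treatment codes reviews AAT data before any planned efficacy analysis. A case would probably be seen, but the reviewer would have no visible rule to apply.

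**Conclusion.** The gap is real in the visible text and is low priority. If a subject restarts augmentation and a later AAT value falls in a Day 7, 14 or 28 window, that arm's estimate is biased by k/8 or k/16 residual SDs. A placebo case moves all three comparisons. Every arm's interval at the affected visit widens, by a factor of 1.10 to 1.85 for a shift of 3 to 10 SDs in an arm of 8.

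Two stronger readings are not supported:

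- A reader might infer that intervals widen at every visit. Under the specified unstructured covariance they widen at the affected visit or visits only. All visits are reached only if augmentation restarts before Day 7 or the compound-symmetry fallback is used.
- A reader might infer a general inflation of false-positive findings. The simulated rates are conditional on a rare event and on assumed µM values. For 500 mg there is little or no inflation, because the same value also enlarges the SD.

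The frequency cannot be derived from the documents. Inclusion criterion 8, exclusion criteria 9 and 22, the prohibition and the 28-day treatment period all work against the event.

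**What to change.** 1. In SAP 9.3.1.2 and 9.3.2.2, set to missing any post-baseline AAT value drawn within 42 days after an augmentation dose, mirroring the baseline rule. If the non-public windowing rules or appendices already do this, a cross-reference is enough.
2. Flag such values at the AAT data review by the biostatistician without treatment codes (protocol 10.7.1).
3. If a case occurs, report an analysis that keeps the values as a supplementary treatment-policy analysis. It is not a check of the missing-at-random assumption.
4. Reconcile protocol 9.1.2 with 9.1.4 and Table 3-3 footnote e on which visits follow early stopping. The choice is the sponsor's.

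The cost is two SAP sentences or one cross-reference, one extra model run only if needed, and one protocol clarification. No new data are required: protocol 9.6 already records medication start and stop dates, and the restart date alone suffices. The downside is a few more missing values, about 1–5% on the standard error for one lost Day 28 value, and reliance on missing at random. That assumption is open to question for a subject who restarted because of worsening disease.
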